6.4.3.1 Patient's assessment of PsA pain intensity

The patient's assessment of pain will be performed using 100 mm visual analog scale (VAS) ranging from "no pain" to "unbearable pain" after the question "Please indicate with a vertical mark (|) through the horizontal line the most pain you had from your psoriatic arthritis today".

6.4.3.2 Patient's global assessment of disease activity

The patient's global assessment of disease activity will be performed using 100 mm VAS ranging from "very good" to "very poor", after the question "*Considering all the ways psoriatic arthritis affects you, please indicate with a vertical mark (|) through the horizontal line how well you are doing today*".

6.4.3.3 Health Assessment Questionnaire (HAQ-DI)

The HAQ-DI© was developed by Stanford University and is one of the most widely used measures to assess the long-term influence of chronic disease on a subject's level of functional ability and activity restriction. The disability assessment component of the HAQ, the HAQ-DI, assesses a subject's level of functional ability and includes questions of fine movements of the upper extremity, locomotor activities of the lower extremity, and activities that involve both upper and lower extremities. There are 20 questions in eight categories of functioning including dressing, rising, eating, walking, hygiene, reach, grip, and usual activities. The stem of each item asks over the past week "Are you able to ..." perform a particular task. Each item is scored on a 4-point scale from 0 to 3, representing normal (normal, no difficulty [0]), some difficulty (1), much difficulty (2), and unable to do (3).

The purpose of the HAQ-DI in this study is to assess the functional ability of patients with PsA.

[figure not shown]
6.4.3.4 Medical Outcome Short Form Health Survey (SF-12) Version 12

The SF-12v2[®] Health Survey is a shorter version of the SF-36v2[®] Health Survey that uses just 12 questions to measure functional health and well-being from the patient's point of view.

Taking only two to three minutes to complete, the SF-12v2[®] is a practical, reliable and valid measure of physical and mental health and is particularly useful in large population health surveys or for applications that combine a generic and disease-specific health survey. The SF-12v2[®] covers the same eight health domains as the SF-36v2[®] with one or two questions per domain.

As the survey uses norm-based scoring, comparisons can be made among the other generic health surveys such as SF-36v2 and it can measure outcomes concisely at the population level, and it is a widely used tool for monitoring population health, comparing and analyzing disease burden and predicting medical expenses.

The purpose of the SF-12 in this study is to assess the HRQoL of patients. Given the acute nature of this disease, version 2, with a 1-week recall period, will be used in this study.

6.4.4 Physician's global assessment of disease activity

The physician's global assessment of disease activity will be performed using 100 mm VAS ranging from no disease activity to maximal disease activity, after the question "*Considering all the ways the disease affects your patient, draw a line on the scale for how well his or her condition is today*". To enhance objectivity, the physician must not be aware of the specific patient's global assessment of disease activity, when performing his own assessment on that subject.

[figure not shown]
6.4.5 High Sensitivity C-reactive protein (hsCRP)

Blood for this assessment will be obtained in order to identify the presence of inflammation, to determine its severity, and to monitor response to treatment.

Since the results of this test may unblind study personnel, results from the central lab will be provided for screening and baseline only. The hsCRP results from samples collected during the treatment period will be revealed following database lock only.

6.4.6 Erythrocyte sedimentation rate (ESR)

ESR tests MUST be performed locally. Blood for ESR, which is helpful in diagnosing inflammatory diseases and is used to monitor disease activity and response to therapy, will be obtained at scheduled visits as indicated in [Table 6-1](#).

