Obtain informed consent	X																				
Inclusion/exclusion criteria	X	X	X																		
Demographics	X																				
Psoriasis/PsA medical history / previous therapies	X																				
Relevant medical history/current medical conditions	X																				
Washout evaluation/instruction	X																				
PsA CASPAR criteria		X																			
Smoking and alcohol history			X																		
Cardiovascular medical history	X																				
Physical Exam ⁴		X	X	X	X	X	X	X	X	X	X	X	X	X	X	X	X	X	X		
Height		X																			

[figure not shown]

Weight		X	X							X									X			
Vital signs		X	X	X	X	X	X	X	X	X	X	X	X	X	X	X	X	X	X	X		X
Chest X-ray ⁵		X																				
ECG		X																				
Prior/Concomitant medication/ non-drug therapy	X	X	X	X	X	X	X	X	X	X	X	X	X	X	X	X	X	X	X	X		X
Randomization via IRT			X																			
Administration of sc study treatment via PFS at study site			X	X	X	X	X	X	X	X	X	X	X	X	X	X	X	X	X			
Adverse Events/SAEs ³ (incl. injection site reaction & occurrence of infections)	X	X	X	X	X	X	X	X	X	X	X	X	X	X	X	X	X	X	X	X	X	X
QuantIFERON TB-Gold test		X																				
Hematology, blood chemistry ⁶		X	X						X	X			X				X			X		
Serum pregnancy test		X																				
Urinalysis/Urine pregnancy test ⁷			X				X		X	X		X		X		X			X			
Anti-CCP	X																					
Rheumatoid factor (RF)	X																					
High sensitivity C-Reactive protein (hsCRP)		X	X	X			X	X	X	X	X	X	X	X	X	X	X	X	X	X		
Erythrocyte Sedimentation Rate (ESR) ⁷		X	X	X			X	X	X	X	X	X	X	X	X	X	X	X	X	X		
Tender and swollen joint		X	X	X			X	X	X	X	X	X	X	X	X	X	X	X	X	X		

Responder Status Assessment ⁹										X	X	X	X	X	X	X	X	X		
Treatment period 1 completion form										X										
Treatment period 2 completion form																		X		

¹ If washout period is ≤ 4 weeks, visit 1 & visit 2 can be performed the same day
² Patients who discontinued prematurely or withdrawn during a specific treatment period should return for a final visit. The final visit should be scheduled approximately four (4) weeks after the last study treatment, and should be performed before any new treatment is initiated
³ AEs/SAEs occurring after informed consent has been obtained must be reported. Patients who **discontinued prematurely** should be contacted **via telephone** to collect AE/SAEs information. Any AE/SAEs that occur in the following 84 days (12 weeks) after last dose of study drug must be reported.

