⁴ These assessments are source documented only and will not be entered into the eCRF
⁵ Not necessary if done within past 3 months. If not, should be scheduled only after patient has met inclusion/exclusion criteria
⁶ Fasting sample
⁷ Tests performed locally using kits supplied by central lab
⁹ Those patients on secukinumab 150 mg who are non-responders at Week 16, 28, or 40 will start receiving secukinumab 300 mg s.c. every 4 weeks up to Week 48.

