6.4.2 Tender 78 joint count and swollen 76 joint count

Joint counts will be performed by the assessor(s) who must be well trained and part of the site personnel. Whenever possible, the same evaluator should perform these assessments at all visits.

The 78 joints assessed for tenderness include the 2 temporomandibular, 2 sternoclavicular, 2 acromioclavicular joints, 2 shoulders, 2 elbows, 2 wrists, 2 first carpometacarpal, 10 metacarpophalangeal, 10 proximal interphalangeal, 8 distal interphalangeal joints of the hands, the 2 hip, 2 knee, 2 talo-tibial, 2 mid-tarsal, 10 metatarsophalangeal, 10 proximal interphalangeal, and 8 distal interphalangeal joints of the feet. All of these except for the hips are assessed for swelling. Joint tenderness and swelling are to be graded present (1) or absent (0). Synovial fluid and/or soft tissue swelling but not bony overgrowth represents a positive result for swollen joint count. Dactylitis of a digit in the foot or hand counts as one tender and swollen joint.

Data is recorded for tender and swollen joints (right or left side), i.e. a box (no, yes or not applicable) needs to be ticked for all joints. The total number of tender and swollen joints (right and left) will be automatically calculated in the eCRF.

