2.5 Analysis of the primary objective

The primary objective is to demonstrate that the efficacy of secukinumab 300 mg at Week 16 is superior to placebo in patients with active PsA based on the proportion of patients achieving an American College of Rheumatology 20 (ACR20) response.

A patient will be considered as improved according the ACR20 criteria if she/he has at least 20% improvement in the two following measures:

- Tender joint count,
- Swollen joint count.
- and at least 20% improvement in at least 3 of the following 5 measures:

- a. Patient's assessment of pain,
- b. Patient's Global Assessment of Disease Activity,
- c. Physician's Global Assessment of Disease Activity,
- d. Health Assessment Questionnaire (HAQ) score,

e. Acute phase reactant (high sensitivity C-reactive protein (hsCRP) or ESR) Primarily, CRP will be used to calculate ACR response. ESR will only be used in the event CRP is

missing.

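### On-treatment hsCRP is withheld from sites because it may unblind, but ESR is run locally at the same visits with no rule keeping it from the staff who score joints and the physician's global

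*Protocol*

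**What the plan says.** On hsCRP, Protocol 6.4.5 states: "Since the results of this test may unblind study personnel, results from the central lab will be provided for screening and baseline only". It adds: "The hsCRP results from samples collected during the treatment period will be revealed following database lock only".

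On ESR, Protocol 6.4.6 states: "ESR tests MUST be performed locally". The same section says that ESR "is used to monitor disease activity and response to therapy, will be obtained at scheduled visits as indicated in" Table 6-1. The ESR footnote in that table reads "Tests performed locally using kits supplied by central lab".

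On who scores, Protocol 6.4.2 states: "Joint counts will be performed by the assessor(s) who must be well trained and part of the site personnel". The rationale for Amendment 1 records that an independent joint assessor is no longer required, and the current 6.4.2 agrees. Protocol 6.4.4 keeps the patient's global from the physician who scores the physician's global, and does not mention ESR.

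On use in the analysis, SAP 2.5 takes CRP first for the ACR acute-phase domain and says "ESR will only be used in the event CRP is" missing.

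**The concern.** The protocol treats an on-treatment acute-phase reactant as able to reveal the arm, and acts on that for hsCRP. Protocol 6.4.1 lists hsCRP and ESR as alternatives within one ACR domain, and 6.4.6 describes ESR as a marker of response to therapy. A plan that masks one and leaves the other at the site needs either a matching rule or a reason why ESR differs. It gives neither.

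At stake are the items that site staff score. A 20% improvement in both the tender and the swollen joint count is mandatory for ACR20, and the physician's global is one of the five further domains. The two joint counts alone also classify 150 mg patients as responders or non-responders at Weeks 16, 28 and 40, and so determine which treatment group they are reported under in Treatment Period 2. A scorer who has seen a patient's ESR fall could, without intending it, score that patient more favourably. If ESR falls more often on active drug, that error would favour the active arms.

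**Working it through.** **1. Are the visits the same?** In Table 6-1 the rows for hsCRP, ESR and tender/swollen joints share one pattern: Visits 2, 3, 4 and 7 to 19. After baseline and up to the primary time point, these are Weeks 1, 4, 8, 12 and 16. By the Week 16 scoring, a site can therefore hold four earlier on-treatment ESR values (Weeks 1, 4, 8 and 12) besides that day's result. A rule on same-day order alone would not hide the earlier trend.

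**2. Does any passage close the route?**

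| Place | What it protects | Covers ESR? |
|---|---|---|
| Protocol 5.4 | Commits to blinded site staff and assessors; the methods are confidential randomization data and look-alike syringes | No |
| Protocol 6.4.2 | Trained site assessor, the same one where possible | No |
| Protocol 6.4.3 | Patient questionnaires come before investigator evaluations | No |
| Protocol 6.4.4 | Patient's global hidden from the physician | No |
| Protocol 6.4.5 | On-treatment hsCRP withheld | hsCRP only |
| Protocol 6.4.6 and the Table 6-1 footnote | Local test with supplied kits | No reader named, no order against scoring |
| SAP 2.5 | ESR as fallback for missing CRP | Analysis use only |

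**3. How much of ACR20 is exposed?** Site staff score the tender count, the swollen count and the physician's global. Pain, patient's global and HAQ are completed by the patient before any investigator evaluation, and the fifth domain is primarily CRP, which is masked. Both mandatory conditions and one of the five domains are exposed. A responder still needs 3 − 1 = 2 further domains that staff do not score.

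**4. The plan's own sample size.** With 20% v 50%, 2:1 allocation, two-sided 0.05 and 90% power, the pooled rate is (0.20 + 2 × 0.50)/3 = 0.40. The uncorrected placebo number is [1.960 × √(1.5 × 0.40 × 0.60) + 1.2816 × √(0.20 × 0.80 + 0.50 × 0.50/2)]² / 0.30² = 38.4, so 39. With continuity correction it is (38.45/4) × [1 + √(1 + 6/(38.45 × 2 × 0.30))]² = 43.3, so 44, and 88 on 300 mg. This matches the plan. After 10% loss, 44/0.9 and 88/0.9 give 49 and 98, which the plan rounds to 50 and 100. Masking ESR changes none of this.

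**5. Illustration on assumed shifts.** The documents give no size for the leak. Suppose the true ACR20 rate is 20% in both arms, with 100 patients on 300 mg and 50 on placebo, and biased scoring adds d to the 300 mg rate only. The statistic is z = (p₁ − p₀)/√[p(1 − p)(1/100 + 1/50)], where p is the pooled rate. The continuity-corrected version first subtracts ½(1/100 + 1/50) = 0.015 from the difference. Summing the exact binomial probabilities of all outcomes with z > 1.96 gives:

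| Assumed shift d | Uncorrected | Continuity-corrected |
|---|---|---|
| 0 points | 2.3% | 1.2% |
| 3 points | 5.7% | 3.3% |
| 5 points | 9.5% | 6.0% |
| 10 points | 25.4% | 18.8% |

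These figures show how sensitive a two-proportion test at this sample size is to scoring bias. They do not estimate the bias, and the planned primary test is a covariate-adjusted logistic regression.

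**The case against.** A reader might infer that the blind is broken. The documents do not support that. They say only that ESR is done locally. They do not say that assessors see the result, that it is read before scoring, or that it reveals the arm.

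A reader might also take the figures above as the trial's false-positive risk. That fails too. The scenario needs a drug that lowers ESR enough to hint at the arm while doing nothing for ACR20. Protocol 3.3 reports ACR20 of 50.0% v 17.3% and 51.0% v 15.3% for 150 mg against placebo in two phase 3 trials. A shift of 3 to 10 points in the whole composite is an assumption, and step 3 limits how far staff scoring alone can move it.

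It is also tempting to say that ESR is hardly needed and could be dropped. SAP 2.5 names it as the fallback for missing CRP, and the Protocol summary lists it among the efficacy assessments. SAP 2.13 is not in the public text, so other uses cannot be ruled out.

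Finally, strict withholding is hard to run. Under Protocol 8.2 the investigator certifies the eCRF data. There are two database locks, so withholding until lock would be unclear. The rationale for Amendment 1 says that sites are unlikely to have an independent assessor for each evaluation.

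All of this limits the size of the point and shapes the remedy. It does not remove the inconsistency: one acute-phase reactant is masked for a stated reason, and its alternative is not.

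**Conclusion.** The point holds as an unprotected route that departs from the protocol's own masking standard. It is not evidence of unblinding. It can affect the two mandatory joint counts, the physician's global, and the Week 16, 28 and 40 responder classification. It does not reach the patient-reported domains in the same way, because those are completed first.

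The size is unknown. It depends on whether scorers see ESR, how far ESR separates the arms, and how far that knowledge moves a score; the documents give none of the three. With the large effect assumed for the primary comparison (50% v 20%), a small bias would be more likely to distort the estimated odds ratio than to decide the test by itself. The change is worth making because it is cheap and gives ESR protection in line with what hsCRP already has.

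**What to change.** Add to Protocol 6.4.6:

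- At each post-baseline visit, the joint counts and the physician's global are completed and recorded before that visit's ESR is read.
- Earlier post-baseline ESR values are kept out of the scorers' view when they score.
- Where staffing allows, the person who runs the kit, and not a scorer, reads and enters the result.

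Keep ESR collection at every scheduled visit, so that the SAP 2.5 fallback for missing CRP remains available.

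The cost is a short protocol addition, a site instruction and a minor change in the order of work at visits. No extra staff are required, and the sample size, significance level and analysis do not change. Masking stays incomplete where the same investigator scores and later certifies the eCRF.

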6.4.8 DAS28 and EULAR response

The DAS28 is a measure of disease activity based on Swollen and Tender Joint Counts, ESR or CRP and the Patient Global Assessment. A DAS28 score > 5.1 implies active disease, ≤ 3.2 low disease activity, and < 2.6 remission. EULAR response criteria are based on DAS28 status in combination with DAS28 improvements.

6.4.9 Psoriatic Arthritis Disease Activity Score (PASDAS)

PASDAS is a new composite measure developed to assess disease activity in Psoriasis (GRACE Project) ([Helliwell 2012](#)). It is calculated by utilizing seven measures; the seven components are: Patient reported measures (excluding mental component summary score (MCS) of the medical outcomes survey Short Form-36 (SF-36-PCS)), skin, peripheral joint counts (Tender and Swollen joint counts), Dactylitis (LDI), [REDACTED] acute phase response (CRP) and Patient & Physician global VAS scores.

$$\begin{aligned} \text{PASDAS} = & (0.18 \times \sqrt{\text{Physician global VAS}}) \\ & + (0.159 \times \sqrt{\text{Patient global VAS}}) \\ & - (0.253 \times \sqrt{\text{SF36-PCS}}) \\ & + (0.101 \times \text{LN}(\text{Swollen joint count} + 1)) \\ & + (0.048 \times \text{LN}(\text{Tender joint count} + 1)) \\ & + (0.23 \times \text{LN}(\text{Leeds Enthesitis Count} + 1)) \\ & + (0.377 \times \text{LN}(\text{Dactylitis count} + 1)) \\ & + (0.102 \times \text{LN}(\text{CRP} + 1)) + 2) \times 1.5. \end{aligned}$$

VAS for PASDAS assessment:

Instruct patients to place marks on the lines below to indicate answer to the following questions relating to the past week.

Global Disease Activity: The patient's assessment of PSORIASIS and ARTHRITIS will be performed using 100 mm VAS ranging from "Excellent" to "Poor" after the question

"Considering all the ways PSORIASIS and ARTHRITIS affects you, please indicate with a vertical mark (|) through the horizontal line how well you are doing over the past week".

6.4.10 Minimal disease activity

The proportion of patients achieving minimal disease activity (MDA (Coates 2010) (5 of the 7 following: ≤ 1 tender joint count, ≤ 1 swollen joint count, PASI ≤ 1 or IGA ≤ 1 , patient pain VAS ≤ 15 , patient global VAS ≤ 20 , HAQ-DI ≤ 0.5 , tender enthesal points ≤ 1).

6.4.11 Dactylitis Assessments

[REDACTED]

[REDACTED]

Presence of dactylitis

If dactylitis is present with any finger or toe, the subject is counted as a subject with dactylitis.

6.4.12 Enthesitis Assessments

Presence of enthesitis:

If enthesitis is present with any of the 18 sites below, the subject is counted as a subject with enthesitis.

- Medial epicondyle humerus (left/right (L/R))
- Lateral epicondyle humerus (L/R)
- Supraspinatus insertion into greater tuberosity of humerus (L/R)
- Greater trochanter (L/R)
- Medial condyle femur (L/R)
- Quadriceps insertion into superior border of patella (L/R)
- Patellar ligament insertion into inferior pole of patella or tibial tubercle (L/R)
- Achilles tendon insertion into calcaneum (L/R)
- Plantar fascia insertion into calcaneum (L/R)

[REDACTED]

[REDACTED]

6.4.14 Psoriasis Area and Severity Index (PASI)

The PASI assessment will be conducted for patients in whom at least 3% of the body surface area (BSA) was affected by psoriatic skin involvement at BL. The PASI assesses the extent of psoriasis on four body surface areas (head, trunk and upper and lower limbs) and the degree of plaque erythema, scaling and thickness. A PASI score ([Fredriksson and Pettersson 1978](#), [Weisman 2003](#), [Gottlieb 2005](#)) will be derived as indicated in [Table 6-2](#).

The head, trunk, upper limbs and lower limbs are assessed separately for erythema, thickening (plaque elevation, induration), and scaling (desquamation). The average degree of severity of each sign in each of the four body regions is assigned a score of 0-4. The area covered by lesions on each body region is estimated as a percentage of the total area of that particular body region. Further practical details help the assessment:

The neck is assessed as part of the head.

The axillae and groin are assessed as part of the trunk.

The buttocks are assessed as part of the lower limbs.

When scoring the severity of erythema, scales should not be removed.

Table 6-2 The PASI scoring system

Body region	Erythema (E)	Thickening (plaque elevation, induration)(I)	Scaling (desquamation) (D)	Area score (based on true area %)(A)*
Head (H)**	0=none 1=slight 2=moderate 3=severe 4=very severe	0=none 1=slight 2=moderate 3=severe 4=very severe	0=none 1=slight 2=moderate 3=severe 4=very severe	0 = 0% 1 = 1-9% 2 = 10-29% 3 = 30-49% 4 = 50-69% 5 = 70-89% 6 = 90-100%
Trunk, (T)***	0=none 1=slight 2=moderate 3=severe 4=very severe	0=none 1=slight 2=moderate 3=severe 4=very severe	0=none 1=slight 2=moderate 3=severe 4=very severe	0 = 0% 1 = 1-9% 2 = 10-29% 3 = 30-49% 4 = 50-69% 5 = 70-89% 6 = 90-100%
Upper limbs (U)	0=none 1=slight 2=moderate 3=severe 4=very severe	0=none 1=slight 2=moderate 3=severe 4=very severe	0=none 1=slight 2=moderate 3=severe 4=very severe	0 = 0% 1 = 1-9% 2 = 10-29% 3 = 30-49% 4 = 50-69% 5 = 70-89% 6 = 90-100%
Lower limbs (L)****	0=none 1=slight 2=moderate 3=severe 4=very severe	0=none 1=slight 2=moderate 3=severe 4=very severe	0=none 1=slight 2=moderate 3=severe 4=very severe	0 = 0% 1 = 1-9% 2 = 10-29% 3 = 30-49% 4 = 50-69% 5 = 70-89% 6 = 90-100%

* Percentage (not score) of body region (not whole body) affected will be entered in the eCRF

**Neck is assessed as part of the Head (H) body region.

***Axillae and groin are assessed as part of the Trunk (T) body region.

****Buttocks are assessed as part of the Lower limbs (L) body region.

Because the head and neck, upper limbs, trunk and lower limbs correspond to approximately 10%, 20%, 30% and 40% of the body surface area, respectively, the PASI score is calculated using the formula:

$$PASI = 0.1 (E_H + I_H + D_H)A_H + 0.2 (E_U + I_U + D_U)A_U + 0.3(E_T + I_T + D_T)A_T + 0.4(E_L + I_L + D_L)A_L$$

where E = erythema, I = induration, S = scaling, and A = area,

H = Head, U = Upper limbs, T = Trunk, and L = Lower limbs

PASI scores can range from a lower value of 0, corresponding to no signs of psoriasis, up to a theoretic maximum of 72.0. The investigator is only responsible for collecting the components or scoring signs and total regional area. More information is provided in [Appendix 6](#).

